Human Subjects Involvement, Characteristics, and Design

Aim 3 will involve a randomized pilot test (RPT) of DIPPer Academy. We propose to enroll up to 50 parents of young children with T1D into the RPT. Parents who participate will be randomized to either an immediate treatment or a control group. Parent will be recruited via letter, telephone call, or in clinic. Parents will be asked to give written informed consent for their participation and permission to obtain a measure of HbA1c level in their child. Parents will be asked to complete study assessments (online surveys) at Time 1 (baseline), Time 2 (post-treatment), and Time 3 (follow up). We will collect child HbA1c at Times 1, 2, and 3. We anticipate that parents may spend about 3 hours completing the DIPPer Academy curricula spread out across 14 weeks of treatment. We expect the surveys at Times 1, 2, and 3 will each time take about 20 minutes to complete.

All parents regardless of gender, race, ethnicity, and socioeconomic class will be considered potentially eligible to participate. Specific inclusion criteria for parents are:

1. Parents of a young child who is between 3-5 years old and at least 3 months post T1D diagnosis.
2. Parents who are English-speaking.

Parent exclusion criteria for are:

1. Young children with evidence of type 2 diabetes or monogenic diabetes.
2. Parents with evidence of severe psychiatric disorder.
3. Young children with a comorbid chronic illness (e.g., renal disease) that requires ongoing care beyond T1D.
4. Young children with a history of anemia or medication use that may interact with glycemic control (e.g., systemic steroids).
5. Young children with an HbA1c $\leq 7.5\%$ (which is the current ADA target).⁶

Sources of Materials

For all participating parents, we will collect demographic data and medical history data specific to T1D. We will also collect data via parent surveys and usage data collected during the intervention (i.e., website use statistics). Survey and parent usage data will be entered and stored in an electronic database (REDCap). This database will be located on a secured server maintained by the Department of Biostatistics at KUMC. No one outside of the research team will have access to data identifying the families who participated. We will obtain a measure of child HbA1c.

Potential Risks

The overall risks of participation in this project are no more than minimal.

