Before the proposed projects begin, we will obtain approval from the Institutional Review Board (IRB) at Children's Mercy Hospital (CMH). The PI will also secure approval from her home institution, the University of Kansas Medical Center, to Rely on the IRB at CMH as the IRB of record for the projects. In compliance with regulatory practices, the PI and Co-Investigators will secure "continuing approval" for the research projects each year from the CMH IRB and will notify the CMH and KUMC IRB's if any Adverse Events (AEs), Other Reportable Information and Occurrences (ORIOs), and Unanticipated Problems Involving Risks to Subjects or Others (UaPs) occur in the conduct of the projects. The PI (with the assistance of Co-Investigators, as needed) will assume primary responsibility for reporting AEs, ORIOs, UaPs, or unforeseen outcomes to the IRBs in a timely fashion and will promptly inform the study sponsor of any action taken by the IRB at CMH because of continuing review. The proposed research designs have been developed keeping in mind how to maximize specific data collection and minimize risk to parents (i.e., psychometrically sound and benign questionnaires, [name] availability to provide medical supervision of patients). However, at the discretion of the CMH IRB, the PI will recruit a Data Safety and Monitoring Board (DSMB) to oversee and monitor the data collection and intervention delivery. We propose members of the DSMB will include an endocrinologist, a psychologist, and a certified diabetes educator. If a DSMB is requested by the CMH IRB, we propose that the DSMB will meet at least annually by teleconference. For each of these meetings, the PI and the biostatistician will jointly prepare a summary of the following topics:

Performance monitoring: A report of subject recruitment/retention, protocol adherence, and quality of data collection procedures.

Safety monitoring: A review of safety of the participants, including confidentiality and any adverse events or side effects related to the study procedures.

STATISTICAL ANALYSIS PLAN

Hypotheses:

Hypothesis 1: DIPPer Academy will result in better Time 2 HbA1c than standard of care controlling for Time 1 measurements.

Hypothesis 2: DIPPer Academy will result in improvements in HbA1c across time (a decreasing time trend for HbA1c).

Hypothesis 3:

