Hypothesis 4: DIPPer Academy will result in greater reported Time 2 parent self-efficacy and lower reported post-treatment parenting stress, mealtime behavior problems and hypoglycemia fear than standard of care, controlling for Time 1 measurements on these variables.

Data Analyses. For the primary outcomes, we will conduct a sensitivity analysis to test for any effects due to attrition. We will also use an intent-to-treat strategy and imputation model to examine parent data even if they are lost to attrition. For all analyses, we will include parental depression as a covariate if determined to be correlated with our outcome variables. To test for between group differences in glycemic levels (Hypothesis 1), we will conduct an ANCOVA with Time 2 (post-treatment) score as the outcome, group (treatment vs. control) as focal predictor, and Time 1 (baseline) score as covariate. In addition, we will calculate within group standardized effect sizes (in SD units) and within-group changes for HbA1c based on Time 1 and Time 2 values. To estimate and test time trends in glycemic levels for DIPPer participants (Hypothesis 2) we will use appropriate generalized mixed models with a random parent intercept to account for clustering of repeated measures within parents. Finally, to test for post-treatment differences between groups in reported parent self-efficacy, parenting stress, mealtime behavior problems, and hypoglycemia fear (Hypothesis 3) we will calculate within group standardized effect sizes (in SD units) and within group changes for parents' PSESDM, PIP, BPFAS, and HFS-PYC scores using parents' Time 1 and Time 2 data. To test for statistical significance, we will conduct an ANOVA for each variable as described above for Hypothesis 1.

REFERENCES

1. Liese, A.D., et al., *The burden of diabetes mellitus among US youth: prevalence estimates from the SEARCH for Diabetes in Youth Study*. Pediatrics, 2006. **118**(4): p. 1510-8.
2. Vehik, K., et al., *Increasing incidence of type 1 diabetes in 0- to 17-year-old Colorado youth*. Diabetes Care, 2007. **30**(3): p. 503-9.
3. Dabelea, D., *The accelerating epidemic of childhood diabetes*. Lancet, 2009. **373**(9680): p. 1999-2000.
4. Patterson, C.C., et al., *Incidence trends for childhood type 1 diabetes in Europe during 1989-2003 and predicted new cases 2005-20: a multicentre prospective registration study*. Lancet, 2009. **373**(9680): p. 2027-33.

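### Hypothesis 2 names only a random parent intercept; with independent residuals and correlation that falls over time, its HbA1c trend test would run at about 6-12%, not 5%

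*Combined protocol and SAP*

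**What the plan says.** Under Human Subjects Involvement, Characteristics, and Design, the protocol says "We propose to enroll up to 50 parents of young children with T1D into the RPT". Parents are "randomized to either an immediate treatment or a control group", with no allocation ratio. It also says "We will collect child HbA1c at Times 1, 2, and 3". Treatment lasts 14 weeks. Time 3 is labelled as follow-up and has no date. Children with HbA1c at or below 7.5% are excluded.

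In the SAP's Hypotheses list, Hypothesis 2 is worded as "a decreasing time trend for HbA1c". Under Data Analyses it is tested in DIPPer participants only, using "appropriate generalized mixed models with a random parent intercept to account for clustering of repeated measures within parents". No random slope, residual covariance, robust standard error, coding of time, contrast, significance level or sidedness is given.

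The other HbA1c analyses stop at Time 2: the Hypothesis 1 ANCOVA takes Time 2 as its outcome, and the descriptive summary covers "within-group changes for HbA1c based on Time 1 and Time 2 values".

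**The concern.** A random intercept with independent residuals implies one common correlation for every pair of visits. Repeated measurements on a child are often less alike the further apart they are. If that is so for HbA1c here, the Time 1-Time 3 difference varies more than the model allows. Its standard error is then too small and its p-value too low. The hypothesis is worded as a decreasing trend, so a linear slope is the natural reading, and with equally spaced visits the slope is the Time 1-Time 3 contrast. At stake is a fall in HbA1c within the treated arm declared significant more often than the nominal level permits.

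**Working it through.** The plan gives no power, SD, correlation or error rate for Hypothesis 2, so there is no stated figure to reproduce.

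**Inputs**
- From the protocol: three HbA1c occasions, up to 50 parents, Time 2 after 14 weeks of treatment.
- Assumed: equal allocation (50/2 = 25 treated children), complete data, normal HbA1c, two-sided 5%, no covariates, and the correlations shown.

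**Formula.** Let r12, r23 and r13 be the true correlations and m = (r12 + r23 + r13)/3. Under the random-intercept model the Time 1-Time 3 difference is given variance proportional to 1 - m. Its true variance is proportional to 1 - r13. So

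R = (1 - r13)/(1 - m), and actual size = 2 x [1 - Phi(1.96/sqrt(R))].

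**Worked case.** AR(1) with adjacent correlation 0.7: r13 = 0.49 and m = (0.70 + 0.70 + 0.49)/3 = 0.63. R = 0.51/0.37 = 1.378, and 1.96/sqrt(1.378) = 1.67, so size = 9.5%. The model standard error is 1/sqrt(1.378) = 0.852 of the true one, about 15% too small.

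| Adjacent / Time 1-Time 3 correlation | R | Actual size |
|---|---|---|
| 0.70 / 0.70 (exchangeable) | 1.000 | 5.0% |
| 0.80 / 0.78 | 1.065 | 5.7% |
| 0.70 / 0.65 | 1.105 | 6.2% |
| 0.50 / 0.25 (AR(1)) | 1.286 | 8.4% |
| 0.70 / 0.49 (AR(1)) | 1.378 | 9.5% |
| 0.90 / 0.81 (AR(1)) | 1.462 | 10.5% |
| 0.85 / 0.65 | 1.615 | 12.3% |

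Simulation of the slope test (n = 25, 40,000 trials per case, t reference with 49 degrees of freedom) agrees to within about half a point.

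**Variations**
- AR(1) plus 20% independent visit noise: 6.6-7.5% at equal spacing.
- Time 3 assumed at week 26 or 40: 8.4-11.5% without noise, 6.8-8.2% with it. The most uneven case tried (week 66, correlation 0.9 at a 14-week lag) reached 12.9%.
- REML fits with 20% lost at Time 3: 8.0% and 11.5% at AR(1) 0.6 and 0.8 (600 trials each, Monte Carlo error about 1.2 points).

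**Other tests from the same model.** With Time 3 at equal spacing, week 26 or week 40, the overall two-degree-of-freedom visit test runs at 4.9-6.3%. Contrasts between adjacent visits are mostly conservative.

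**The replacement.** With complete data, the Time 1-Time 3 contrast from an unstructured covariance is a paired t test (24 degrees of freedom). It held 4.7-5.3% in simulation.

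**Price in power.** Take a steady fall reaching 0.5 SD at Time 3, with exchangeable correlation 0.7. The noncentrality is 0.5/sqrt(2 x 0.3/25) = 3.23. Power is 88.6% for the random-intercept slope and 87.2% for the replacement. Under AR(1) 0.7 it is 78% against 66%, but the 78% belongs to a test running at 9.5%.

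**What the replacement leaves in place.** Suppose the 7.5% exclusion acts on the Time 1 value and a share p of children is eligible. Before selection, HbA1c is normal with SD 1. Selected children average phi(z)/p above the population mean, where z = Phi^-1(1 - p). With no true change, the expected fall by Time 3 is (1 - r13) x phi(z)/p. For p = 0.8, phi(z)/p = 0.35. The spurious fall is 0.51 x 0.35 = 0.18 SD under AR(1) 0.7, and 0.30 x 0.35 = 0.105 SD if exchangeable at 0.7. As p goes from 0.9 to 0.6, the corrected Time 1-Time 3 test rejects in about 8-39% of null trials (AR(1) 0.7) or 6-24% (exchangeable 0.7).

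**The case against.** The strongest reply is that this is under-specification, not a demonstrated error. The SAP asks for appropriate models, and nothing in the sentence rules out a residual structure, a random slope or visit as a factor. Inflation needs four things together: independent residuals, decaying correlation, a slope or Time 1-Time 3 test, and a 5% level. The documents state none of them. That stands, and it keeps the finding conditional. It does not remove it, because the random intercept is the only structure named, and covariance and contrast should be fixed before the data are seen.

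Two stronger readings are tempting and not supported.
- A reader might infer that the follow-up HbA1c has no planned use, or that the plan fails for lack of a Time 2-Time 3 comparison. Hypothesis 2 can already use Time 3, and no visible hypothesis claims that a change is maintained. The Hypothesis 3 entry in the Hypotheses list is blank and may be removed text, although Data Analyses attaches that number to the survey outcomes: "mealtime behavior problems, and hypoglycemia fear (Hypothesis 3) we will calculate within group standardized effect sizes". A Time 2-Time 3 contrast is a useful description, not a required test.
- A reader might infer that an unstructured covariance makes Hypothesis 2 a clean 5% test of the intervention. It repairs the standard error, but selection on high HbA1c can move a single-arm mean with no treatment effect. If eligibility is judged on an earlier value than Time 1, that effect would be smaller; the protocol does not say which value is used.

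**Conclusion.** The point holds in conditional form. Fitted as named with independent residuals, a linear-trend or Time 1-Time 3 test runs at about 6-12% when correlation falls with lag, and at 5% when it does not. Very mild decay sits at the bottom of that range; steep decay or very uneven spacing sits at the top or slightly beyond. The figures assume 25 treated children, complete data and a two-sided 5% level. The documents do not supply the alpha, correlation, allocation ratio or Time 3 date, and they do not show that the trial's test will in fact be inflated.

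Priority is low. The SAP does not rank its hypotheses, but this is a within-arm analysis in a pilot. Minimization of Risks, item 3, describes the HbA1c purpose as exploratory, and the randomised Time 2 ANCOVA is unaffected.

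**What to change.** Replace the Hypothesis 2 sentence in the SAP with wording to this effect: HbA1c in DIPPer participants will be modelled with visit (Times 1, 2, 3) as a factor and an unstructured 3 x 3 within-child covariance, by REML with Kenward-Roger degrees of freedom. Hypothesis 2 is tested by the Time 1-Time 3 contrast, two-sided 5%. If the model does not converge, a random-intercept model with small-sample cluster-robust standard errors will be used. The Time 2-Time 3 change may be reported with a 95% confidence interval, as description only.

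State the Time 3 date. Add that, because children at or below 7.5% HbA1c are excluded, a fall within the treated arm may be regression to the mean; the Hypothesis 2 result is not by itself evidence of a treatment effect, which rests on the between-group Time 2 ANCOVA.

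The cost is wording only, with no new data. The model has nine parameters (three means, six covariance terms) instead of four, and loses one to two points of power if correlation is exchangeable. If visits are unequally spaced, the target changes slightly, from a slope to the change between Time 1 and Time 3.
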